## 3 RESEARCH METHODS

### 3.1 Study Design

This is a multi-country, non-interventional cohort study using routinely collected data from healthcare databases to evaluate the effectiveness of OM-85 for prevention of recurrent RTIs in paediatric and adult patients, and its use in routine practice. The study utilises secondary data from healthcare databases of two European countries (Belgium and Italy) and China, extracting data from the THIN databases in Belgium and Italy and from the Inspur database in China.

As primary objectives, the effectiveness of OM-85 is assessed through (1) a *before-after design*, comparing the rate of RTI episodes before and after initiation of OM-85 (primary objective 1), and (2) a *comparative effectiveness design*, comparing the rate of RTI episodes during follow-up (at 12 and 24 months) between patients who initiated OM-85 and patients who did not initiate OM-85 (primary objective 2).

The patients who did not initiate OM-85 serve as a SOC/non-user comparator group. The secondary objectives include describing the baseline characteristics of patients who initiated OM-85 and the SOC/non-user group, pattern of prescribing OM-85, and patterns of prescribing antibiotics and concomitant medications of interest during follow-up. The objectives will be studied separately in each study country.

The TTE was used as the framework for the design (28,29) of this non-interventional study. The key elements of a hypothetical target trial were defined (eligibility criteria, treatment strategies, treatment assignment, outcomes, follow-up, causal contrasts, and statistical analysis), and the corresponding design elements were defined for this non-interventional cohort study using the healthcare databases (Appendix 6). All elements of the TTE framework are applicable for the comparative effectiveness objectives (primary objective 2, secondary objective 4, and exploratory objectives CCI). For the remaining objectives of the study, the elements of the TTE framework utilised include the eligibility criteria to define the study population, treatment strategies to define which exposure groups are investigated, and treatment assignment to define how patients are classified to each treatment strategy (i.e., exposure group).

The overall study population will include patients  $\geq 1$  year of age with  $\geq 1$  RTI episodes, and no prescriptions of bacterial lysates within 12-months prior to the inclusion (baseline period) (Section 3.2.1). Within the overall study population, patients will be categorised to one of the two exposure groups (treatment strategies): patients who initiated OM-85 at the CED or within 30 days after the CED (i.e. 30-day initiation grace period), and SOC/non-user group who did not initiate OM-85 at CED or within the 30-day initiation grace period (Section 3.3.1).

[figure not shown]
To emulate randomisation and enhance the comparability of the exposure groups at baseline, the SOC/non-user group will be restricted to patients with similar prognostic factors and probability of receiving OM-85 at CED, by matching on PS.

The study period will start from the date of earliest data availability and end at the date of latest data availability in each of the data sources ([Section 3.2.1](#)). The outcomes will be assessed at 3, 6, 9, 12, and 24 months after the CED, as per data availability.

The study design, including time windows for defining key variables, is summarised in [Figure 1](#).

**Figure 1 Study Design**

Note: CED: cohort entry date; RTI: respiratory tract infection; SOC: standard of care

-  For the patients who initiate OM-85 during the initiation grace period, another index date is assigned at the date of the 1st OM-85 prescription: OM-85 initiation date. This date is used as the index date in analyses on exclusively OM-85 initiators.
-  Outcomes defined for each objective are listed in [Table 7](#) and [Table 8](#).
-  Pregnancy at CED is estimated using a variable assessment window expanding from 183 days (6 months) before CED to 280 days (9 months) after CED, as detailed in [Section 3.2.2.3](#).
-  Selected covariates are defined during initiation grace period, to be used in sensitivity analysis for clone censor weighting.

period (see [Section 3.3.3](#)).

### 3.1.1 Rationale for the Study Design

Three countries (Belgium, Italy and China) were chosen to have representativeness of routine practice in Europe and China, the two geographical areas of interest. The inclusion of three countries additionally ensures a wide coverage of time, and of different settings of care. Moreover, including three countries increases the total number of patients included in the study.

The use of secondary data from healthcare databases aims to maximise the number of patients included in the analysis. Before starting the study, a robust data source feasibility assessment was carried out to understand the availability of data in the real-world data sources and to assess the suitability of these data sources for examining the study objectives. The robust feasibility involved an assessment of availability of variables of interest, the degree of completeness of key variables, tentative patient count using preliminary inclusion criteria, and operational factors that can affect the conduct of the study.

The study will include patients with recurrent RTIs initiating treatment with OM-85 (new users), to prevent the risk of prevalent user bias (or healthy-user bias). However, no active new user comparator could be identified ([Section 3.3.1.1](#)); therefore, the comparator will be a SOC/non-user group. PS matching will be applied to improve the comparability of the exposure groups, where candidate variables for the PS include age, sex, type and number of previous RTI episodes, selected comorbidities, and healthcare visits ([Section 3.3.3](#)).

This non-interventional study is designed utilising the TTE framework ([28,29](#)), as increasingly recommended in the scientific community ([30,31](#)) and by regulators ([32](#)), to avoid biases non-interventional studies are prone to, especially time-related biases. Indeed, in this study aligning the CED and treatment initiation is challenging, because treatment initiation cannot be required at CED, as it would lead to very few patients in the OM-85 group. Therefore, the initiation grace period is applied, as recommended in TTE ([28,29](#)) and applied in prior studies ([33,34](#)). The TTE framework is utilised for the comparative effectiveness objectives, where outcomes in the exposure groups are compared in follow-up. Additionally, the other objectives of the study will be assessed in the same study population and exposure groups, as they are free of time-related biases.

A before-after design among patients initiating OM-85 will also be utilised to provide reference data on differences in study outcomes before and after OM-85 therapy. The minimum of 12 months of baseline data for observing RTIs is secured for each patient.

## 3.2 Setting

### 3.2.1 Study Periods

The study periods for each country are summarised in [Table 1](#). The study periods were defined based on the feasibility assessment: in each country, the study period start at the earliest data

availability and ends at the latest date of data availability. The exposure of interest, OM-85, was marketed in these countries throughout the study period.

**Table 1 Study Time Periods in Belgium, Italy and China**

	Total study period Belgium: January 2005  – July 2024 Italy: January 1994  – July 2024 China: January 2018  – July 2024		
Time before the inclusion period enables a minimum 12-month baseline period for the first included patient	Inclusion period: occurrence of CED Belgium: January 2006 – June 2022 Italy: January 1995 – June 2022 China: January 2019 – June 2022	Initiation Grace Period: A 30-day initiation grace period starting from the CED to allow the included patients to initiate OM-85 during a reasonable period after the CED.	Time after the initiation grace period enables a 24-month follow-up for the last included patient

Note: CED: cohort entry date

 For THIN Belgium, the total study period starts from the first data availability from 2005.

 For THIN Italy, the total study period starts from the first availability of the general practice data from 1994 onwards (paediatrician data from 2017).

 For INSPUR China, the total study period starts from the first availability of reliable electronic data in the database from 2018 onwards.

In each country, the study period will include an inclusion period, a baseline period, an initiation grace period and a follow-up period. These are defined for each included patient:

- **Inclusion period:** The inclusion period, when patients are included to the study in the respective countries, are described in [Table 1](#). The inclusion period will start at least 12 months after the start of the study period, to enable a 12-month baseline period for all included patients. The inclusion period will end 24 months before the end of the study period, to allow a 24-month follow-up time for the last included patient.
- **CED:** The CED is defined during the inclusion period, as the date of the 2nd, 3rd, ... or nth RTI episode during the inclusion period (see inclusion criteria in [Section 3.2.2](#)). This is also the date when a patient fulfils all the eligibility criteria. The CED can occur any time during the inclusion period. If a patient meets the eligibility criteria more than once during the inclusion period, and thereby has several candidate CEDs, the CED used in the study will be selected at random, which is one of the unbiased methods of selection of index date (29). The CED defines the end of the baseline period and the start of the initiation grace period for each included patient.

- **Baseline period:** The baseline period for each included patient is defined as the time before the CED. The minimum baseline period will be 12 months, and the maximum baseline period will be as long as data are available in each country (from January 2005 in Belgium, from January 1994, for GPs and 2017 for paediatricians, in Italy, and from January 2018 in China). The minimum baseline period of 12 months will be used for assessing the RTI rate during the baseline period and other baseline variables ([Section 3.7.4.1](#)). The maximum baseline period (all available data) will be used for selected variables, such as comorbidities (e.g., allergies, myocardial infarction, and cancer, see [Table 8](#)), since these could have occurred earlier but may not have been recorded in the data during the 12-month baseline period. Extending the 12-month baseline period for such variables is expected to improve the accurate classification of them (i.e., decreases the risk of covariate misclassification).
- **Initiation grace period:** For each included patient, a 30-day initiation grace period starting from the CED will be applied, to allow the included patients to initiate OM-85 during a reasonable period after the CED, as it is unrealistic to expect that OM-85 would in clinical practice be prescribed on the date of meeting the eligibility criteria ([28,29](#)).
- **OM-85 initiation date:** The OM-85 initiation date will be the date of the first observed prescription of OM-85 during the 30-day initiation grace period, starting from the CED. This is applicable only for the OM-85 exposure group.
- **Follow-up period:** The follow-up for each included patient will start from the end of the 30-day initiation grace period for comparative effectiveness analysis and will continue until end of the study period or until censoring ([Table 2](#)), whichever occurs first.
- **Censoring during follow-up:** Patients in the SOC/non-user group are censored at the date of initiating OM-85 ([Table 2](#)).

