### 3.2.2 Study Population

The overall study population will include patients  $\geq 1$  year of age with  $\geq 1$  RTI episodes and no prescriptions of bacterial lysates within 12 months prior to inclusion to the study. Additionally, included patients will be required to have  $\geq 12$  months of continuous enrolment in the database prior to inclusion. The inclusion criteria are detailed in [Table 4, Section 3.2.2.1](#). No exclusion criteria are applied for this study.

The CED is the date of the 2nd, 3rd, ... or nth RTI episode, i.e., the date of fulfilling this inclusion criterion. During the inclusion period, patients can have several CEDs. For patients with several CEDs, the CED of the patient used in the study will be selected randomly, which is one of the unbiased methods to select the date (29). Thus, each patient can enter the study only once.

Patients in the overall study population will be categorised to one of the two exposure groups (treatment strategies): patients who initiated OM-85 at the CED or during the 30-day initiation grace period, and SOC/non-user group of patients who did not initiate OM-85 at the CED or during the 30-day initiation grace period.

The primary and secondary objectives and the exploratory objectives **CCI** will be studied in the overall study population ([Table 3](#)). The exploratory objectives **CCI** **CCI** **CCI**. The sub-populations applied in this study are further described in [Section 3.2.2.3](#).

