**Table 4 Inclusion Criteria**

	Inclusion Criteria	Operational Definition
1	Patient aged $\geq 1$ year of age at CED	Aged $\geq 1$ year at CED
2	Patient has $\geq 1$ RTI episodes during the 12-month baseline period prior to CED	$\geq 1$ RTI episodes within a 12-month period during the inclusion period. The CED is the date of the 2 nd , 3 rd , ... or n th RTI episode (i.e., date of fulfilling the inclusion criteria). If one patient has multiple CED during the inclusion period, the CED will be selected randomly. The definition of an RTI episode provided in Section 3.3.2.1
3	Patient has $\geq 12$ months of continuous enrolment in the database prior to CED	$\geq 12$ months of continuous enrolment in the database prior to the CED. Operationally, patients were required to have entered the database at least 12 months before the CED to be included in the study. In THIN (Belgium and Italy), this can be defined by a district variable for entry to the database: first contact date. In Inspur (China), patients are required to have records in the database at least 12 months before the CED (during the 12-month baseline period) to be eligible for inclusion
4	No record of a prescription of any bacterial lysates in the 12-month baseline period prior to CED	No record of the country-specific drug codes ( Appendix 4 ) during the 12-month baseline period

Note: CED: cohort entry date; RTI: respiratory tract infection; THIN: The Health Improvement Network.

Inclusion criterion 2 on the requirement of having  $\geq 1$  prior RTI episodes is important to apply because OM-85 is indicated for prevention of recurrent RTIs (24). However, patients in the SOC/non-user comparator group may still have fewer prior recurrent RTIs than the OM-85 group receiving preventive therapy. Therefore, prior recurrent RTIs will also be used in the PS matching of the compared exposure groups. The impact (preventive effect) of OM-85 on the recurrence of RTIs is anticipated to be higher in patients with an increased recurrence risk (35). Hence, the analyses will also be stratified by the number of RTI episodes prior to CED (see [Table 5](#)).

The inclusion of patients is not defined by sex. Sex is instead defined at CED and considered in the PS.

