### **3.4.1 The Health Improvement Network: Belgium and Italy**

THIN® is a large European database of fully anonymised, non-linkable and non-extrapolated Electronic Health Records collected at the physicians' level. These anonymised patient-level data are obtained from a network of voluntary physicians. In Belgium and Italy, no ethics submission is needed for the current study. An ethics submission to access data from THIN is mandated in case study results will be published. In such case, THIN will submit an ethical application via the THIN Euroboard.

THIN Belgium covers information from GPs and has information on > 500,000 patients per year, with an average follow-up of 9 years. THIN Italy covers information from GPs and has information on > 550,000 patients per year, with an average follow-up of 7 years. The feasibility assessment found that overall, the variables required to address the primary objectives are well captured and of good completeness in both THIN Belgium and THIN Italy, with the exceptions of vaccine administration, lung function tests, and hospitalisation data. Lung function data will therefore not be collected, and vaccination data will be limited to influenza vaccinations. As information is collected from GPs only, the information on healthcare resource utilisation is not complete. Date of birth is captured as year of birth and therefore age in the first year of life cannot be assessed with further granularity than this.

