### 3.5 Study Size

In this non-interventional study, all patients available in the databases will be included in the study population. Based on the feasibility assessment, 14,362 patients meeting inclusion criteria and using OM-85 are available in Belgium (of which 10,555 patients aged  $\geq 18$  years old), 3,219 patients in Italy (of which 2,742 patients aged  $\geq 18$  years old), and 8,656 patients in China (of which 1,338 patients aged  $\geq 18$  years old). The study size is based on including the maximum number of patients for the OM-85 group. However, the strategy to include patients to this study using the TTE framework is not identical to the feasibility assessment, and fewer OM-85 exposed patients will be included in this full study using the TTE framework ([Section 3.9.5](#)).

For primary objective 1, the study size required to estimate the difference between rates of two groups (pre- and post- OM-85 treatment) is evaluated based on the precision of the point estimate, as described below.

The CI for point estimate of incidence rate ratio (IRR) is calculated as follows ([38](#)), where a and b are the counts of events in each group, PT1 and PT2 are the person-time (in person-years [PYs]) in each group, and F is a quantile of the F distribution.

$$\widehat{\text{IRR}} \text{ CI} = \left( \frac{PT_2}{PT_1} \right) \left( \frac{a}{b+1} \right) \frac{1}{F_{\alpha/2, 2(b+1), 2a}} \text{ to } \left( \frac{PT_2}{PT_1} \right) \left( \frac{a+1}{b} \right) F_{\alpha/2, 2(a+1), 2b}$$

With a hypothetical population rate of 2 episodes per person per year in the baseline (based on reported Upper RTI global age-standardised incidence rate of 225,505 per 100,000 person-years, in the Global Burden of Diseases, Injuries, and Risk Factors Study [GBD] 2019 ([39](#))), and assuming equal person-time in the two groups, the width of the 95% CI for the estimated IRR under difference effect sizes and sample sizes are demonstrated in [Table 9](#).

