### **3.9.5 Risk of Random Error**

The precision of the RTI episode rates depends on a range of parameters, including the number of patients included in the study, the average follow-up time available for the patients, and the rate of loss to follow-up. The risk of random error increases and the precision of the rates decreases (i.e., the CIs become wider) with fewer included users of OM-85 and comparator patients, less follow-up time per patient, and/or higher rate of patients lost to follow-up. The risk of random error will be discussed with reporting the results of the study, considering the number of patients included in the analysis and the available follow-up time. However, the data source feasibility assessment showed that the average follow-up time in the selected data sources would allow the analysis at the selected time points with no significant loss to follow-up, which would limit the risk of random error.

At the same time, the strategy to include patients to this study using the TTE framework is not identical to the feasibility study. Specially, the feasibility study did not apply the TTE framework where all patients meeting the inclusion criteria are followed during the initiation grace period, to define in which treatment strategy patients are categorised to. The feasibility study included all patients ever prescribed OM-85 meeting preliminary inclusion and exclusion criteria. In the TTE framework applied here, only patients who initiate OM-85 within 30 days of meeting inclusion criteria (i.e. CED) are included. Additionally, when patients with multiple candidate CEDs will be included to the study population by choosing one CED randomly, there is risk that some OM-85 users will be included to the study as non-users (based on that CED; another CED not selected could be the one leading to OM-85 use). Therefore, fewer OM-85 exposed patients will be included in this full study using the TTE framework. Even though using the TTE framework is a compromise to study size, it minimises bias and improves the internal validity of the study.

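### Drawing one cohort entry date at random from a patient's eligible RTIs, combined with the 12-month lysate washout, tilts the SOC group toward few follow-up RTIs and biases the primary objective 2 rate ratio against OM-85

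*Protocol*

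**What the plan says.** Section 3.2.1 defines the CED as the date of a second or later RTI episode in the inclusion period. Section 3.2.2 adds "During the inclusion period, patients can have several CEDs". For such patients "the CED used in the study will be selected at random, which is one of the unbiased methods of selection of index date", and section 3.2.2 concludes "Thus, each patient can enter the study only once". Appendix 7 repeats the rule and the claim of unbiasedness.

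Criterion 4 in Table 4 restricts the candidates: "No record of a prescription of any bacterial lysates in the 12-month baseline period prior to CED".

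The primary outcome is the rate of RTI episodes. Primary objective 2 compares it between the groups at 12 and 24 months, from day 30 after the CED. Section 3.9.5 accepts that, under the random draw, "there is risk that some OM-85 users will be included to the study as non-users". It treats this as a loss of study size and says that the framework minimises bias. Selection on later RTIs is not mentioned.

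**The concern.** Drawing an index date at random is harmless when the number of eligible dates does not depend on the outcome. Here every outcome event can itself be an eligible date. A CED is kept with probability 1/K, where K is the patient's number of candidates, and K includes RTIs that fall in the follow-up of that same CED.

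If this acted equally in both groups, both rates would be lowered alike and a null ratio would stay near 1. The washout makes it unequal, because a SOC patient's RTIs in the next year count toward K and an OM-85 starter's do not. At stake is the comparative primary estimate, which is shifted upwards so that OM-85 looks less effective than it is. A larger sample only makes the shifted estimate more precise.

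**Working it through.** **The plan's own figures.** The protocol gives no number for the effect of the draw and no sample size for primary objective 2. The only yardstick is Table 9, for primary objective 1: an IRR of 0.9, called a small effect, with a CI width of 0.197 at 350 person-years. It reproduces. At 2 per year, b = 2 × 350 = 700 and a = 0.9 × 700 = 630. The F-quantile interval is 0.807 to 1.004, width 0.197.

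**Step 1: which RTIs are candidates.**
- After a SOC CED, any RTI in the next 12 months that falls in the inclusion period is automatically a candidate. The CED supplies the required prior RTI, and there is no lysate record unless OM-85 or another lysate is started later.
- After an OM-85 start, criterion 4 bars every RTI in the 12 months after the prescription. As the prescription falls within 30 days of the CED and follow-up starts on day 30, this covers nearly all of follow-up year 1.

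Let c be the patient's other candidates outside that year and n the RTIs within it.
- SOC CED: kept with probability 1/(c + 1 + n), which falls as n rises.
- OM-85 CED: kept with probability 1/(c + 1), which does not depend on n.

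**Step 2: hand calculation.** Take n as Poisson with mean 2, the rate in section 3.5 ("With a hypothetical population rate of 2 episodes per person per year in the baseline"), and hold c fixed. The mean of n among selected SOC CEDs is E[n/(c+1+n)] / E[1/(c+1+n)].
- c = 4: 1.73 instead of 2, so the null ratio is 2/1.73 ≈ 1.15.
- c = 10: 1.85 instead of 2, so the null ratio is 2/1.85 ≈ 1.08.

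This shows the mechanism and why it weakens as the window lengthens. It is not the study's bias, because c is fixed and there is no matching on history.

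**Step 3: simulation.** Windows: China has 3.5 years ("China: January 2019 – June 2022"). Belgium has patients "with an average follow-up of 9 years" and Italy an average of 7 years. With 12 months' baseline and the follow-up taken off, personal windows of about 6–8 years (Belgium) and 4–6 years (Italy) were assumed. RTIs were Poisson, with or without gamma frailty, under the 14-day episode rule and the 12-month washout, with follow-up from day 30. SOC was standardised to the OM-85 group on prior-year RTI count, as perfect matching would do. The true IRR was 1, and SOC censoring was switched off to isolate the draw.

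| RTI rate per year | Window | 12-month IRR, random draw | OM-85 starters kept as OM-85 |
|---|---|---|---|
| 2 | 3.5 years | 1.11–1.14 | 21–26% |
| 2 | 6–8 years | 1.02–1.08 | 10–16% |
| 1 | 3.5 years | 1.18–1.23 | 39% |
| 1 | 8 years | 1.12–1.14 | 21% |
| 0.5 | 3.5 years | 1.34 | 58% |
| 0.5 | 8 years | 1.29 | 38% |

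At 24 months the ratio was 1.00–1.06 at 2 per year and at most about 1.14, at 0.5 per year.

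**Step 4: what causes it.** Under the same null:
- every eligible CED used: 0.99–1.02;
- first eligible CED: 0.97–1.01;
- random draw kept but washout removed: 1.00.

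So the draw and the washout together produce the bias.

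**Step 5: with a real effect.** With a true IRR of 0.8 at 2 per year, the random draw gave 0.94 (3.5 years) and 0.87 (8 years) at 12 months. Under the same conditions all CEDs gave 0.83 and the first CED 0.80–0.83.

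**Step 6: with the protocol's SOC censoring and grace period added,** under the null at 2 per year, the random draw gave 1.16 (3.5 years) and 1.11 (8 years). All or first CEDs gave 1.03, so about 0.03 of the excess is not due to the draw.

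**The case against.** The strongest reply is about size. At the protocol's own rate of 2 per year and personal windows of 6–8 years, the 12-month shift is only a few per cent, and at 24 months it nearly vanishes. The larger values need a lower RTI rate, which the protocol does not state, or China's short window. This stands. A reader might infer that the bias matches the effect of interest throughout. The documents do not support that, since it depends on country and horizon. The only stated effect size, 0.9, also belongs to primary objective 1.

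A reader might also infer that a patient's inclusion depends on future RTIs. Mostly it does not. What depends on them is which eligible CED is kept, and the draw is from eligible RTIs only.

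The loss of OM-85 users might be read as an undisclosed error. Section 3.9.5 discloses it and names the random draw as a cause; it only leaves the loss unsized.

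Finally, the plan has two safeguards for comparability, propensity score matching and a clone-censor-weight sensitivity analysis. Matching uses baseline variables, which cannot undo selection on later RTIs. As written, the clone-censor-weight analysis begins at the same drawn CED, so it inherits the selection.

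**Conclusion.** The concern holds for the comparative primary objective. The protocol's statement that the random draw is unbiased is wrong for this design, because the candidates are outcome events and the washout acts on one group only. The direction is upwards, against OM-85. The 12-month size under no effect is about 1.11–1.14 for China and 1.02–1.08 over 6–8 years at 2 RTIs per year, and larger at lower rates. The 24-month bias is smaller. These sizes rest on assumed RTI rate, frailty, probability of starting OM-85 and personal window; the mechanism and direction follow from the protocol's rules. The source cited for unbiasedness was not available, so nothing is said about what it claims.

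No claim is made that primary objective 1 is affected.

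The draw also keeps only about 10–40% of OM-85 starters as OM-85 at 1–2 RTIs per year. Applied to the feasibility counts at 2 per year, this leaves roughly 0.11 × 14,362 ≈ 1,580 in Belgium, 0.15 × 3,219 ≈ 483 in Italy and 0.23 × 8,656 ≈ 1,991 in China. Requiring a start within 30 days of an RTI reduces these further. At 0.5 per year in a 3.5-year window most starters (58%) are kept, so the loss of a majority is not universal.

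**What to change.** Let every eligible CED enter as its own emulated trial, classified OM-85 or SOC at each. Match within CED calendar period, and bar a patient from being matched to another of their own CEDs, which 1:1 greedy matching would otherwise allow. Cluster standard errors on patient and on matched pair; section 3.7.1 already plans cluster-robust errors. Apply the same entry rule to the clone-censor-weight analysis. Replace the once-only entry rule in section 3.2.2 and Appendix 7, and delete the statements that the random draw is unbiased.

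If one CED per patient must be kept, use the first eligible one. That removes the bias but does not recover the lost OM-85 starts: with the washout in place it kept slightly fewer than the random draw.

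The cost is revised protocol and SAP wording and a larger person-by-CED dataset with repeated patients. No new data are needed.
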